The proposed LLLT protocol will use the Biolase Epic X, an InGaAsP diode laser (940nm) using the pain relief handpiece, a device which has received FDA approval (GUDID 00647529002537) for the treatment of pain, muscle relaxation and healing via increased local circulation. The LLLT will be administered to the experimental group at 30 j/cm^2. The laser will be applied extraorally, on the skin overlying the mandible. Application will be for 40 seconds per side, with 10 seconds administered in four places along the jawline, 1 cm apart starting from the gonial angle. The timing would coincide with standard post-operative care, with the first LLLT administration performed on post-operative day 1, prior to the patient's discharge from the hospital. The follow-up LLLT doses would be given at the standard post-op follow-up visits, at one-week intervals, which would be at week 1, week 2, week 3, week 4, week 5, and week 6. Patients will be seen for evaluation at week 8 and again at approximately 20 weeks post-surgery. The control group will follow the same post-op visit schedule, but receive a dummy treatment in which the laser handpiece is moved over the patient's jaw in a similar fashion as the experimental but without laser irradiation.

Nerve function, pain and swelling will be measured according to objective measures. A baseline measurement will be recorded pre-operatively for nerve function and pain. Baseline for swelling will be used from the final measurement at week 8, due to the changes in mandible length caused by the orthognathic surgery. Measurements for each outcome will also be performed on the days for which

LLLT is administered. The individual who performs the assessment will be blinded to the group to which each patient belongs.

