To evaluate nerve function, three tests will be conducted, a two-point discrimination (TPD) test, a hard stimulus test and soft stimulus test. For the TPD test, the patient will be instructed to close their eyes, and a caliper will be placed on the lateral aspect of the patient's chin. The calipers will start at 0 mm and be incrementally opened in .5mm increments, and the first distance felt by the patient as two distinct points will be recorded reported in millimeters. For the soft- and hard- stimuli tests, the lower face will be divided into eight regions, with four symmetric regions per side. Region 1 will be from the skin on the chin at the midsagittal plane laterally 1 cm. Region 2 will be the skin from the edge of Region 1 extending laterally 1 cm. Region 3 will be the skin from the edge of Region 2 extending laterally 1 cm. Region 4 will be the vermillion of the lower from the midsagittal plane to the commissure. The regions will be designated by an "L" for left or "R" for right, plus a number as per the above scheme. Each region will be checked for nerve function via two tests, a cotton-swab test and a two test. During the evaluation, the patient will be instructed to keep their eyes closed. The cotton-swab test will involve the skin in each region being lightly brushed in a 2cm vertical path twice per region, and the patient reporting if they feel the contact. Likewise, the toothpick test will involve the skin being slightly depressed by the edge of a toothpick in three spots separated by 1 cm each per region, and the patient reporting if they feel the contact. The responses will be recorded as positive or negative for soft (swab) or hard pressure (toothpick), by region.

Pain will be reported via use of a visual analogue scale (VAS). The patient will rate the intensity of the pain on each side of the mandible at each visit. The intensity of the pain will be from zero, meaning complete absence of pain, to 10, indicating the maximum amount of pain imaginable.

Swelling will be measured with a soft measuring tape from the tip of the chin to the lower lobe of the ear, bilaterally. The calculation of the swelling index will be done by subtracting the baseline length (from the six-week post-operative visit) to the measured length and dividing the difference by baseline length and multiplying by 100.

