### **Sample Size**

Published data (13-15) examining the effect of LLLT on IAN functional recovery shows a range of improvement versus placebo. The percentage of recovery shows that the LLLT treatment led to 27.3% (n=30, not split mouth, standard deviation not reported) (13), 13% (n=12, split mouth,  $7.4167 \pm 1.62$  vs  $8.5000 \pm 1.56$ ) (14), and 15% (n= 15,  $5.12 \pm 0.59$  vs  $5.97 \pm 0.45$ ) (15) improvement in sensory function, with . Additionally, one non-placebo controlled study of patients with long-standing documented neurosensory alteration following dental surgery (12) showed 33% improvement over baseline (n=4).

Using these studies, a sample size graph (Figure 1) was plotted in R Stats Package with the effect size versus sample size, with the standard deviation set to 0.5 and power set to 0.9. In order to detect an effect size of 0.5 with a SD of 0.5 at 90% power a sample size of just over 22 is needed. Therefore, 23 subjects per arm is required.

[figure not shown]

Figure 1- Effect size vs. Sample size.

The oral surgery clinic at Jacobi Medical Center treats approximately 50 patients with orthognathic surgery of the mandible annually, and has done so routinely for the last decade. Recruiting 46 patients to participate, even accounting for potential drop outs or failure to follow-up, should prove feasible.

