### **Informed Consent**

Patients who express interest in volunteering for the study will have the risks and benefits of the study explained to them, as well as that they may be assigned to either a control or experimental group. The details of study participation will be explained, including that the patients will not have any aspect of their surgery or post-care altered, other than LLLT treatment. It will be explained that the time commitment of the study is the same as the normal post-op care, with the exception of two additional visits at 8 weeks and 20 weeks post-op. It will be explained that patients may decide to not volunteer and their treatment will not be affected. Likewise, if the patients decide to drop out of the study, their treatment will not be affected. Information security will also be discussed with the patient during the consent process. All information in the discussion will be provided to the patient in written form, with a copy for them to keep. Patients who desire an alternate language will be offered translation services.

Patients over 18, will be given an informed consent form to sign. Patients who are under 18 will be asked to sign the informed consent form, to indicate their assent, while a legal guardian, who will also be present for the discussion of the risks and benefits of the study, will be asked to sign for consent.

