### **Data analysis**

The primary outcome, change in neurosensory deficit, is measured by the three clinical tests, TPD, soft-stimulus and hard-stimulus. For TPD, the difference between the LLLT group and placebo group at each time point will be compared using an independent t-test, with alpha set at .05. The soft- and hard-stimulus tests for each region will be analyzed at each time point with a chi-square test. VAS pain score and swelling index will be analyzed using independent t-tests for the measurements on each side at each time point, with alpha set at .05. Linear regression will be performed to analyze the relationship of the pain, swelling and nerve tests with age, skeletal class, direction and magnitude of mandibular movement, and inclusion of genioplasty.

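### The swelling index depends on one late post-operative visit, so a patient without that visit drops out of every swelling t-test, including post-operative day 1

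*Combined protocol and SAP*

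**What the plan says.** The Study Design section treats swelling differently from the other outcomes. For those, "A baseline measurement will be recorded pre-operatively for nerve function and pain". For swelling, "Baseline for swelling will be used from the final measurement at week 8", because the operation itself changes the length of the mandible.

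The index is defined a few paragraphs later by "subtracting the baseline length (from the six-week post-operative visit) to the measured length" and "dividing the difference by baseline length and multiplying by 100". The same section therefore names two baseline visits, week 8 and week 6.

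Swelling is measured on both sides on each treatment day. These run from post-operative day 1 ("with the first LLLT administration performed on post-operative day 1") through the weekly visits to week 6. Evaluations follow at week 8 and at about 20 weeks. Informed Consent says the time commitment equals normal care, "with the exception of two additional visits at 8 weeks and 20 weeks post-op".

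For the analysis, the Data analysis section says "VAS pain score and swelling index will be analyzed using independent t-tests for the measurements on each side at each time point". No section gives a rule for a missing baseline length. The Sample Size section calls recruitment of 46 patients feasible, "even accounting for potential drop outs or failure to follow-up", but gives no dropout rate and adds no patients for it.

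**The concern.** The baseline length enters every value of the index, and it is measured weeks after the early visits it is used to interpret. A patient who attends day 1 and the first weeks but not the baseline visit has recorded tape lengths and no computable index. For pain and two-point discrimination, a patient who leaves loses only the later visits. For swelling, the earlier ones go as well.

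Two things are at stake. Usable measurements are discarded in a trial with 23 patients per arm. The day-1 and early-week comparisons also become conditional on attendance well after randomisation. If non-attendance is related to swelling, and differently so in the two arms, the comparison is no longer protected by randomisation.

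**Working it through.** **Inputs.** From Study Design: index at visit t = 100 × (L_t − B)/B, with L_t the tape length and B the late baseline length; lengths on day 1 and at weeks 1-6, on two sides; B at week 8 or week 6. From Sample Size: 23 per arm. The documents give no dropout rate, swelling SD or swelling effect, so those below are assumptions.

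**1. The plan's own figure.** An effect of 0.5 with SD 0.5 is a standardised difference of 1.0. A two-sided t-test at 5% with 90% power needs 22.02 per arm, rounded up to 23, which matches the plan. That calculation concerns nerve function. It contains nothing on swelling and no allowance for loss.

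**2. Values lost per patient**, if all earlier visits were attended:
- Week 8 baseline: day 1 and weeks 1-6 are 7 visits × 2 sides = 14 values.
- Week 6 baseline: day 1 and weeks 1-5 are 6 visits × 2 sides = 12 earlier values. Here a patient who attends week 6 and misses only week 8 loses no earlier value.

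**3. Patients lost per swelling test**, assuming 10% or 20% miss the baseline visit: 0.10 × 23 = 2.3 and 0.20 × 23 = 4.6 per arm. If the loss is random, the standard error of the difference rises by 1/√0.9 = 1.05 or 1/√0.8 = 1.12. With whole patients, 20 or 18 per arm remain. Borrowing the plan's nerve-function standardised difference of 1.0 purely for illustration, t-test power falls from 91.2% (23 per arm) to 86.9% (20) or 83.0% (18). This applies at every swelling time point, day 1 included.

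**4. Bias.** Let a share p of an arm lack the baseline, and let their true mean index exceed that of the retained patients by k. The full-arm mean is (retained mean) + p·k, so the retained mean is too low by p·k. The error in the laser-minus-control difference is p_C·k_C − p_L·k_L. Assume true day-1 means of 6% (laser) and 8% (control), so a difference of −2.0, and k = 3 points (one assumed SD of 3):

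| Loss related to swelling in | p = 0.10 | p = 0.20 |
|---|---|---|
| control arm only | −2.0 + 0.3 = −1.7 | −2.0 + 0.6 = −1.4 |
| laser arm only | −2.0 − 0.3 = −2.3 | −2.0 − 0.6 = −2.6 |
| both arms equally | −2.0 | −2.0 |

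The effect can be understated, overstated or unchanged. Nothing in the documents selects a row.

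**5. Scale of a log-length analysis.** With 6% and 8%, 100 × (ln 1.06 − ln 1.08) = −1.87, not −2.0. A log contrast must be back-transformed within each arm: 100 × (exp(ln 1.08) − 1) = 8, and likewise 6, giving −2.0.

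**The case against.** The strongest points on the other side are these.

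- **The late baseline is a reasoned choice.** Surgery changes mandible length, so a pre-operative length would not serve. This stands, and the fix keeps a late baseline.
- **Week 8 is not settled.** If the six-week visit is the baseline, it is a routine and treatment visit. The argument that a study-only visit is easier to miss then falls away, and fewer patients should be affected. This stands. That argument applies only under the week 8 statement, whereas the loss of all earlier values holds under both.
- **The data are not destroyed.** Tape lengths remain on file. The Outcomes section describes swelling by the tape measurement, and the planned regression mentions swelling without confining it to the index. This stands, but the between-arm t-tests are specified on the index, and those are what lose patients.
- **Losses may be few.** Safety monitoring withdraws patients with clinically significant adverse events but halts the study once more than one has been withdrawn, so that route supplies about two patients at most before a halt. Other loss is anticipated without a rate. The size is therefore unknown.

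A reader might also infer that the laser effect on swelling will be understated. That requires patients with more swelling to leave more often, in a particular pattern across arms, and no section supports it. Nor is the baseline at the end of follow-up: an evaluation at about 20 weeks comes later.

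**Conclusion.** The point holds as a structural weakness in a secondary outcome. Under either stated baseline visit, following the plan as written removes a patient without that visit from every swelling t-test and makes the early comparison conditional on later attendance. The number of values lost per patient (up to 14, or 12 earlier ones) follows from the schedule and the formula alone. The 2-5 patients per arm rest on an assumed 10-20% missing the visit. The power figures also rest on a standardised difference borrowed from the nerve-function calculation. The documents cannot establish the size or direction of bias.

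This does not undermine the primary nerve tests, which do not use the swelling baseline. It is worth correcting because the early lengths exist and the repair is cheap.

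**What to change.** Reconcile the two statements of the baseline visit and keep a late baseline. Then:

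1. **Analyse the recorded lengths.** Fit a repeated-measures mixed model to log tape length at all visits and on both sides, with arm, visit, arm-by-visit and side, and with patient and side within patient as the correlated units. Report the index in each arm as 100 × (exp(visit minus baseline-visit contrast) − 1). Patients without the baseline visit then still contribute their earlier lengths.
2. **Pre-specify a fallback late length** for any index computed per patient: the other of the week 6 or week 8 lengths, or a tape measurement at the existing 20-week visit. Add a sensitivity analysis limited to patients with the primary baseline.
3. **Report the number without the baseline visit, by arm.**

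The cost is a few lines of analysis text and, if chosen, one tape measurement at a visit already scheduled. No patients or visits are added.

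There are downsides. The model assumes that loss is explained by the observed lengths. Fallback baselines mix visit times: with assumed lengths of 130 mm on day 1, 122 mm at week 6 and 120 mm at week 8, the day-1 index is 8/122 = 6.6% or 10/120 = 8.3%, which is why the sensitivity analysis is needed. A fallback also cannot help patients who left before any late measurement; for them only the model uses the early lengths.

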### Participant Recruitment

The patient pool for this study will be drawn from regular patients scheduled to undergo orthognathic surgery at Jacobi Medical Center. Patients who have been cleared for orthognathic surgery already must be in good health and understand the risks of the surgery. The only additional requirements for inclusion are 1) the planned surgery includes bilateral sagittal split osteotomies; 2) patients must be free from pre-operative inferior alveolar neurosensory deficiencies; 3) the patient cannot have an intra-operative

accidental fracture or rupture of the inferior alveolar nerve. The details of the whole orthognathic surgery will be recorded (including maxillary procedure, genioplasty, and direction of positional change of the mandible) but will not alter eligibility for enrolment in the study.

Since 2013, over 30% of the patients treated for orthognathic surgery at Jacobi Medical Center are between the ages of 15 and 18, which is in line with orthognathic surgery in general. As such, the study aims to include these patients in the potential pool of subjects. Because of the significant portion of patients under the age of 18 in general, and their inclusion will allow for age to be examined as a related factor in how healing proceeds. Their inclusion will also allow for an adequate sample size.

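### The two-point discrimination (TPD) test has no stated side, landmark or per-patient summary, although surgery, laser and all other measures are bilateral or by side; measuring both sides at a fixed site and averaging them is a cheap improvement

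*Combined protocol and SAP*

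**What the plan says.** The Study Design section describes the TPD test as follows: "a caliper will be placed on the lateral aspect of the patient's chin", the calipers are opened in 0.5 mm steps, and "the first distance felt by the patient as two distinct points will be recorded reported in millimeters". Left, right or both is not stated. No distance or anatomical landmark fixes the site, and nothing requires the same site at the next visit. The Data analysis section says: "For TPD, the difference between the LLLT group and placebo group at each time point will be compared using an independent t-test". It mentions neither side nor a way to combine sides.

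The other measures are handled by side:

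- Swab and toothpick tests: "the lower face will be divided into eight regions, with four symmetric regions per side", each labelled L or R.
- Pain: "The patient will rate the intensity of the pain on each side of the mandible at each visit".
- Swelling: measured "from the tip of the chin to the lower lobe of the ear, bilaterally".
- Analysis of pain and swelling: "independent t-tests for the measurements on each side at each time point".

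Both sides are operated on in every eligible patient, since Participant Recruitment requires that "the planned surgery includes bilateral sagittal split osteotomies". The laser (or dummy) treatment is also given to each side. The Outcomes section names TPD and the hard and soft stimulus tests together as primary.

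**The concern.** Each patient has two nerves at risk and both sides treated, yet the one continuous primary test is written as a single caliper placement. Three things follow.

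First, the assessor may test a different side, or a different spot on the same side, from visit to visit. The Data analysis section calls the primary outcome a change in deficit, and a baseline is taken before surgery. A patient's change could then be the difference between two nerves that were injured to different degrees.

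Second, a single reading leaves out information from the other side that could be collected at the same visit.

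Third, if both sides are in fact measured, several analyses fit the text: one side, the worse side, the mean, separate left and right tests, or both sides pooled as if they came from different patients. These do not have the same error rate or power, and the choice should not be made after the data are seen. The same gap affects the planned linear regression on the nerve tests, because it is not stated which TPD value enters the model.

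**Working it through.** **Inputs from the Sample Size and Data analysis sections.** Difference 0.5, SD 0.5, power 0.90, 23 per arm, alpha 0.05. Sidedness is not stated; two-sided is assumed, and the one-sided version gives 18 per arm, which does not match the plan.

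**The plan's own figure.** For two independent means the noncentral-t calculation gives n = 22.02 per arm, which agrees with the plan's statement of slightly more than 22 and rounds up to 23. At n = 23 the noncentrality is (0.5/0.5) × √(23/2) = 3.39 on 44 degrees of freedom, and power is 91.2%. This calculation uses one value per patient, so one TPD reading per patient causes no shortfall against the stated target.

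**Mean of two sides.** Let ρ be the correlation between left and right readings in the same patient and arm. The documents do not give ρ, so it is varied. If each side has SD 0.5,

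SD of the mean = 0.5 × √((1 + ρ)/2).

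With the difference kept at 0.5:

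| ρ (assumed) | (1 + ρ)/2 | SD of mean | n per arm for 90% | Power at 23 per arm | Difference detectable at 90% with 23 per arm |
|---|---|---|---|---|---|
| 0.3 | 0.65 | 0.403 | 15 | 98.4% | 0.394 |
| 0.5 | 0.75 | 0.433 | 17 | 96.9% | 0.423 |
| 0.7 | 0.85 | 0.461 | 19 | 94.9% | 0.451 |
| 0.8 | 0.90 | 0.474 | 20 | 93.8% | 0.464 |
| 1 | 1.00 | 0.500 | 23 | 91.2% | 0.489 |

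**Both sides entered as independent observations.** The plan does not propose this, but it does not exclude it. The true variance of an arm mean is then (1 + ρ) times the variance the test assumes. By the normal approximation, the actual type I error is 2 × [1 − Φ(1.96/√(1 + ρ))]:

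- ρ = 0.3: 1.96/1.140 = 1.719, error 0.09
- ρ = 0.5: 1.96/1.225 = 1.600, error 0.11
- ρ = 0.8: 1.96/1.342 = 1.461, error 0.14

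**Separate left and right tests, as planned for pain and swelling.** Two tests at 0.05 give a chance of at least one false positive of 1 − 0.95² = 9.75% per visit if the sides are independent, and less if they are positively correlated.

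**Change of side between visits.** If left and right readings have the same distribution, picking a side at random adds no variance to a comparison of arms at one visit, relative to always testing one fixed side. The cost falls on within-patient change, where baseline and follow-up may come from different nerves. A drifting landmark can add measurement error at any visit. The documents give no figures from which to size either effect.

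**The case against.** The documents do not support four stronger readings that a reader might infer.

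- *Only one side is tested and the other is discarded.* The text is silent on side. One reading is the literal meaning. But every other measure is taken by side, so two-sided TPD with an unwritten summary rule is also plausible. In that case the power gain over a single reading falls away and the defect is the missing rule.
- *TPD drives the sample size.* The Sample Size section speaks of functional recovery and sensory function, names no test and gives no unit. TPD is the only continuous primary test, so the link is a fair guess, but it remains a guess.
- *Switching sides biases the comparison.* The planned test compares arms at each visit and is not a change-score analysis. Allocation is random and the assessor is blinded, so an inconsistent choice of side should not favour either arm.
- *The trial is underpowered because of this.* On the plan's own inputs, one value per patient gives 91.2% power against a target of 90%.

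The power gain is also conditional. The documents do not say whether the SD of 0.5 is per side or per patient; if it already describes a two-side summary, averaging adds nothing to the planned power. If a single reading would have been taken on the worse side, averaging with a milder side could shrink the difference. The patient mean is also not the only valid analysis, since a mixed model with a patient random effect handles the correlation too.

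These objections limit the size of the point. They do not remove it: on either reading, the test and its analysis can be carried out in more than one way.

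**Conclusion.** The point holds as an inexpensive improvement to a primary measure, not as a flaw that undermines the trial. Side, landmark, return to the same site and per-patient summary are all unspecified for TPD, and it is the only measure left without side handling. That conclusion needs no assumption about ρ. The expected harm is noise and a blurred within-patient change, with no expected bias between arms and no shortfall in the stated 23 per arm.

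The gain over a single reading is about 3 to 7 percentage points of power at 23 per arm (from 91.2% to between 93.8% and 98.4%) for ρ from 0.8 down to 0.3, and nothing at ρ = 1. It rests on an assumed ρ, a per-side SD of 0.5 and an equal effect on both sides, and should be read as an illustration. If both sides are already being measured, the value of the fix is a single pre-stated analysis. That avoids the type I error of about 0.09 to 0.14 that comes from treating the sides as independent, and the doubling of tests that comes from analysing each side separately.

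**What to change.** In Study Design, state that TPD is measured on both the left and the right lateral chin, at the same defined site, at every assessment including the pre-operative one, and that each side is recorded. The plan's own L/R region scheme could supply the landmark.

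In Data analysis, state that the TPD value for each patient at each visit is the mean of the two sides, that this single value enters the t-test and the regression, and that the two sides are not entered as independent observations. A mixed model with a patient random effect is an acceptable alternative if it is named in advance.

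The sample size, visit schedule and planned t-test stay as they are. The cost is one extra caliper series at each assessment, if only one side would otherwise have been tested, plus a sentence or two in each section. The documents give no timing for the test, so the added assessor time cannot be stated more exactly.

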### **Outcomes (primary and secondary)**

In this study, the predictor variable was the use of laser therapy versus placebo treatment after orthognathic surgery on the mandible. The primary outcome variable was neurosensory disturbance recovery by the TPD, hard and soft sensory tests. The secondary outcome variables are pain reduction, as measured by change in VAS, and swelling reduction, as measured by soft-ruler measurement of lower face.

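### TPD is scored at the first, unconfirmed report of two points, and none of the three primary sensory tests has catch trials, so false reports enter the primary outcome undetected

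*Combined protocol and SAP*

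**What the plan says.** Study Design sets out the TPD procedure in order. The patient closes their eyes. The steps are given as: "The calipers will start at 0 mm and be incrementally opened in .5mm increments". The TPD score follows from a separate rule, under which "the first distance felt by the patient as two distinct points will be recorded"; the unit is the millimetre. No second application at that opening, repeat or descending run, or single-point application after the start is described.

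For the soft test, each region is "lightly brushed in a 2cm vertical path twice per region, and the patient reporting if they feel the contact". For the hard test, the skin is "slightly depressed by the edge of a toothpick in three spots separated by 1 cm each per region". During these tests "the patient will be instructed to keep their eyes closed". The scoring is: "The responses will be recorded as positive or negative for soft (swab) or hard pressure (toothpick), by region". No application without contact is described, and no rule turns two or three answers into one regional result.

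The same section introduces the outcomes with the statement: "Nerve function, pain and swelling will be measured according to objective measures". Outcomes (primary and secondary) gives these tests their role: "The primary outcome variable was neurosensory disturbance recovery by the TPD, hard and soft sensory tests". Data analysis compares TPD between arms by independent t-test at each time point, and the soft and hard tests by chi-square per region and time point.

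**The concern.** All three tests rest on what the patient says, and the procedure cannot separate sensation from readiness to answer 'two' or 'yes'. In the TPD test the first 'two' ends the series and becomes the score. If it comes below the true threshold, the patient is recorded as having better sensation than is present, and no later step can correct it. A patient with a higher threshold passes through more openings and so has more chances to err. With equal error rates in both arms, that tends to pull the arm means together while spreading the scores.

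The swab and toothpick tests have a related weakness. Every application is a real contact, so a 'yes' from a numb region looks the same as a felt contact.

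The main risk is a diluted treatment effect on the primary outcome. Unconfirmed answers cannot be checked once they have been collected.

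**Working it through.** **The plan's own figure.** Sample Size uses a difference of 0.5, SD 0.5 and 90% power. With two-sided alpha 0.05 (sidedness is not stated), the normal formula 2(z₀.₉₇₅ + z₀.₉₀)²(SD/difference)² gives 21.01. The t-based calculation gives 22.02, which rounds up to 23 per arm and matches the plan. That arithmetic is not in dispute.

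**Inputs for the illustration.** Sample Size cites 7.4167 ± 1.62 vs 8.5000 ± 1.56. I treat these as true thresholds in mm, with a common SD of 1.6 (the mean of 1.62 and 1.56 is 1.59). Without false reports, the standardised difference is (8.50 − 7.42)/1.6 = 0.68. The false-report rate f is not in the documents; 2%, 5% and 10% are assumed, equal in both arms.

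**Chance of at least one false early stop.** The formula is 1 − (1 − f)^k, where k is the number of openings below threshold, counted from 0.5 mm.

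| Threshold | k | f = 2% | f = 5% | f = 10% |
|---|---|---|---|---|
| 7.42 mm | 14 (0.5 to 7.0) | 25% | 51% | 77% |
| 8.50 mm | 16 (0.5 to 8.0) | 28% | 56% | 81% |

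The 0 mm start is in effect a single-point contact, but it always comes first and no rule covers a 'two' there. If such an answer were accepted, k for 8.50 mm would be 17 and the chances 29%, 58% and 83%.

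**Effect on the standardised arm difference (simulation, starting from about 0.68).**

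| Model | f = 2% | f = 5% | f = 10% |
|---|---|---|---|
| First report scored; false reports equally likely at every opening from 0.5 mm | 0.30 | 0.16 | 0.08 |
| Same, but a 'two' at 0 mm can also count | 0.28 | 0.15 | 0.07 |
| First report scored; false reports only within 2 mm of threshold | 0.65 | 0.63 | 0.61 |
| 'Two' needed on both of two applications; independent answers, equally likely at every opening | 0.65 | 0.57 | 0.41 |
| Same, but half of second answers copy the first | 0.40 | 0.26 | 0.15 |

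In the second row at f = 2%, the mean difference falls from 1.08 to 0.77 mm and the SD rises from 1.60 to 2.76, so 0.77/2.76 = 0.28. The SD accounts for more of the loss (1.60/2.76 = 0.58) than the difference does (0.77/1.08 = 0.71).

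In the third row almost every patient meets the same number of exposed openings (2/0.5 = 4). The mean difference is then essentially preserved, and the small loss comes from the SD.

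**Swab and toothpick tests.** Each region gets two real brushes and three real contacts, and no blanks. False positives therefore cannot be counted. Without a combining rule, their effect on the regional result cannot be calculated.

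**The case against.** The strongest objection is that the large losses come from one modelling choice. A patient with an 8.5 mm threshold is made as likely to report a false 'two' at 0.5 mm as at 8 mm. Confining errors to within 2 mm of threshold leaves the difference almost intact. This stands.

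The inputs are also weak. The 7.42 and 8.50 figures have no stated units or test, and the title of that cited study refers to a blink reflex. If they are TPD scores, they are observed values that already contain any response error, so adding more counts it twice. The equal-likelihood model gives a comparator SD of about 2.8 at 2%, against the cited 1.56. For the other cited pair (5.12 ± 0.59 vs 5.97 ± 0.45) it gives an SD of about 1.61 at 2%, well above either cited SD. This also stands: nothing in the documents supports any particular rate.

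The gain from confirmation depends on second answers being at least partly independent of the first. The last row of the table shows how far it shrinks if they are not, which is why single-point trials are needed as well.

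A further objection is that a single run is inferred from silence. That is true, but the procedure is otherwise given step by step, and its recording rule names the first distance.

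Four stronger readings are tempting and are not supported:

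- Patients anticipate because they know the gap only widens. The text does not say what they are told.
- One wrong 'yes' fixes a falsely good swab or toothpick result. No combining rule is given, so this cannot be determined.
- Measurement error runs in one direction only. A false early 'two' can only lower the score, but late reports are also possible and were not modelled.
- Readiness to say 'yes' could pass for nerve recovery in one arm. That needs error rates that differ by arm, for instance through patients guessing allocation, which the sham treatment and maintained blinding are meant to prevent. Assessment is also blinded.

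**Conclusion.** The point holds as a weakness of measurement technique in the primary outcome. The TPD rule accepts an unconfirmed first 'two', and no sensory test includes a catch trial, so false reports are neither limited nor measurable. An early false 'two' lowers that patient's score and adds variance; with equal rates in both arms it tends to dilute the arm difference.

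The size cannot be fixed from the documents. Under the assumptions above, the standardised difference of 0.68 falls to anywhere between about 0.07 and 0.65, depending on the rate and above all on where in the series false reports occur. A reader might infer from the lower figures that the trial loses most of its power; the documents do not support that. The change is worth making because it is cheap and cannot be made after data collection.

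**What to change.** In the TPD paragraph of Study Design, define the threshold as the smallest opening reported as two points on both of two consecutive applications. Intersperse single-point applications at random, and repeat the run once if a single point is called 'two'.

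In the swab and toothpick tests, insert a few no-contact trials, and repeat the region once if a blank is reported as felt.

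Record the number of false reports for each patient and visit, so that the error rate can be seen and compared between arms. Use the identical procedure pre-operatively and at every visit.

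The cost is a wording change and a slightly longer test with the same blinded assessor, caliper, swab and toothpick. Limiting each repeat to one keeps the extra time bounded. The calculated 23 per arm does not change.
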